12 STATISTICAL METHODS

12.1 General Statistical Considerations

Tabulations of summary statistics, graphical presentations, and statistical analyses will be performed using SAS® software. Descriptive statistics will be used to summarize data from this study, including mean, standard deviation, median, minimum, and maximum for continuous variables and frequency distributions and percentages for categorical variables. The specifics for these outputs will be described in detail within the Statistical Analysis Plan (SAP), which will be finalized before database lock.

The last observation prior to the first dose of study medication will be used as the baseline value for calculating post-administration changes from baseline. All data obtained on the eCRF will be presented in by-subject data listings.

Confidence intervals will be at the 95% confidence level unless stated otherwise.

Statistical analyses will be performed using SAS® software or other validated statistical software as required. Details of the statistical analyses will be included in a separate statistical analysis plan (SAP), which will be finalized before the database lock.

12.1.1 *Rationale for Sample Size*

The sample size of 20 subjects is considered adequate on clinical grounds to judge the safety of the combination therapy and obtain an initial estimate of its clinical efficacy.

The primary efficacy endpoint will be the overall response rate (ORR). The ORR for the combination therapy is hypothesized to exceed the value observed with ipilimumab monotherapy (10–15%, [Long et al., 2017](#)). A decision to officially expand enrollment beyond the planned approximately 20 subjects will depend on the number of responders in the first 20 evaluable subjects and will require a protocol amendment. To be considered evaluable, subjects must meet criteria for the Efficacy Evaluable population, be evaluable for tumor response as per RECIST v1.1 at 9 weeks, and have no major protocol deviations.

Evaluability for tumor response will be based on the following:

- Subjects who remain on study until the first evaluation (at 9 weeks) and have a tumor assessment performed.
- Subjects who withdraw from the study due to disease progression before the first evaluation (at 9 weeks) will be considered as subjects with early progression
- Subjects who die from malignant disease before the first evaluation (at 9 weeks) will be considered as subjects with early death

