4 INTRODUCTION

The purpose of this statistical analysis plan (SAP) is to provide comprehensive and detailed descriptions of the methods and presentation of data analyses proposed for RAPT Therapeutics, Inc. Protocol FLX475-03 (Phase 2 Study of FLX475 in Combination with Ipilimumab in Advanced Melanoma). Descriptions of planned analyses are provided in order to avoid post hoc decisions that may affect the interpretation of the statistical analysis. The statistical methods applied in the design and planned analyses of this study are consistent with the International Council for Harmonisation (ICH) guideline *Statistical Principles for Clinical Trials* (E9) (1998).

This SAP will be finalized prior to data analysis and before database lock to provide full details to be presented in the clinical study report (CSR). Any changes between the statistical methods provided in the clinical study protocol and this SAP will be explained herein; any changes or deviations from this SAP relative to the final analysis will be fully documented in the CSR. Minor changes or deviations from the templates for tables, figures, and listings need not be documented in the CSR.

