5 STUDY OBJECTIVES

5.1 Primary Study Objective(s)

The primary objectives of this study are:

- To evaluate the objective response rate (ORR), defined as confirmed complete or partial response per RECIST 1.1, of FLX475 in combination with ipilimumab in subjects with advanced melanoma previously treated with an anti-PD-1 or anti-PD-L1 agent
- To evaluate the safety and tolerability of FLX475 in combination with ipilimumab in subjects with advanced melanoma previously treated with an anti-PD-1 or anti-PD-L1 agent

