7.1.1 Reporting Conventions

Tables and figures will be summarized by treatment group. Tables summarizing demographics and other baseline characteristics will also include a column for all subjects combined. In general, all data collected and any derived data will be presented in subject data listings, for all screened subjects. Listings will be ordered by treatment

group, site, subject number, and assessment or event date. The treatment group presented in listings will be based on the planned assignment, unless otherwise noted.

In general, continuous variables will be summarized to indicate the study population sample size (N), number of subjects with available data (n), mean, SD, median, 25th (Q1) and 75th (Q3) quartiles, minimum, and maximum values. Categorical variables will be summarized by the population size (N), number of subjects with available data (n), number of subjects in each category, and the percentage of subjects in each category. Unless otherwise noted, the denominator to determine the percentage of subjects in each category will be based on the number of subjects with available data. Select ordinal data may be summarized using both descriptive statistics and counts and percentages of subjects in each category, as appropriate.

Non-zero percentages will be rounded to one decimal place. Rounding conventions for presentation of summary statistics will be based on the precision of the variable of summarization, as it is collected in its rawest form (i.e., on the eCRF or as provided within an external file) and are outlined as follows:

- The mean and median will be rounded to one more decimal place than the precision of the variable of summarization;
- Measures of variability (e.g., SD, SE) will be rounded to two more decimal places than the precision of the variable of summarization; and
- Minimum and maximum values will be presented using the same precision as the variable of summarization.

Other statistics (e.g., CIs) will be presented using the same general rules outlined above, or assessed for the most appropriate presentation based on the underlying data.

7.1.2 *Summarization by Visit*

Data summarized by study visit will be based on the nominal, scheduled visit label as reported on the eCRF.

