Data collected at unscheduled visits will not be included in by-visit summaries, but will be considered when endpoint derivations potentially include multiple visits (e.g., determination of baseline value, determination of worst post-baseline value, etc.). All data will be included in subject listings.

7.1.3 *Data Handling Rules*

Unless otherwise noted, values reported as greater than or less than some quantifiable limit (e.g., “< 1.0”) will be summarized with the sign suppressed in summary tables and

figures, using the numeric value reported. Data will display on subject listings to include the sign.

7.1.4 *Standard Calculations*

Where appropriate, the calculated study day of each assessment or event will be presented with the assessment or event date on subject data listings, where study day will be determined as:

- The assessment/event date minus the date of first dose of study drug, if the assessment/event date is prior to the date of first dose; and
- The assessment/event date minus the date of first dose of study drug, plus one, if the assessment/event date is on or after the date of first dose.

Other variables requiring calculations will be derived using the following formulas:

- **Days:** A duration between two dates expressed in days will be calculated using the following conventions:
 - Later date – earlier date + 1, if the earlier date is on or after the date of first dose of study drug; or
 - Later date – earlier date, if the earlier date is prior to the date of first dose of study drug.
- **Months:** A duration expressed in months will be calculated by dividing the duration in days by (365.25 / 12);
- **Years:** A duration expressed in years will be calculated by dividing the duration in days by 365.25;
- **Change from Baseline:** Change from baseline will be calculated as the post-baseline value minus the baseline value;
- **Percentage Change from Baseline:** Percentage change from baseline will be calculated as the change from baseline divided by the baseline value, multiplied by 100.

7.2 *Analysis Populations*

The analysis populations are defined as follows:

- **Full Analysis Set:** All subjects enrolled in the study, also known as the “Intent-to-Treat” (ITT) population.

- **Safety Analysis Set:** All subjects who receive at least one dose of the investigational product, FLX475 (even a partial dose).

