7.4 Efficacy Evaluation

7.4.1 Primary and Secondary Efficacy Endpoints

Primary and secondary efficacy analyses will not be summarized due to early discontinuation of the study and a limited amount of available efficacy data.

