7.7 Changes in the Conduct of the Study or Planned Analyses

The analyses outlined in this SAP include deviations from the protocol as outlined below.

- Efficacy analyses will not be summarized due to early discontinuation of the study and a limited amount of available efficacy data.

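### Confirmed ORR is still a primary objective, yet the SAP gives it no summary result; one footnoted descriptive table would report it without claiming a test

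*SAP*

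**What the plan says.** SAP 5.1 lists as a primary objective "To evaluate the objective response rate (ORR), defined as confirmed complete or partial response per RECIST 1.1". SAP 7.4.1 then states: "Primary and secondary efficacy analyses will not be summarized due to early discontinuation of the study", adding that the available efficacy data are limited. SAP 6.4.1.1 has the same sentence, and SAP 7.7 gives it as the one deviation from the protocol: "Efficacy analyses will not be summarized due to early discontinuation of the study and a limited amount of available efficacy data". This follows the SAP's own rule in section 4: "Any changes between the statistical methods provided in the clinical study protocol and this SAP will be explained herein".

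The protocol had planned more. Section 12.1.6 defines ORR as a proportion with an exact 95% Clopper-Pearson interval. It names the Full Analysis Set (FAS) and the Efficacy Evaluable Set for tumor endpoints, with the Efficacy Eligible Set as a sensitivity analysis. The synopsis makes the Efficacy Evaluable Set the primary basis for ORR. It assigns the FAS to disposition, baseline and exposure. SAP 7.2 keeps only the FAS and the Safety Analysis Set.

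Protocol 11.3.1 requires investigator response assessments on the eCRF at each time point. Protocol 12.1 says: "All data obtained on the eCRF will be presented in by-subject data listings". SAP 7.1.1 is slightly softer: "In general, all data collected and any derived data will be presented in subject data listings, for all screened subjects". It names no response listing.

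**The concern.** Followed as written, the SAP leaves the report with no best-response count, responder proportion or interval for one of the two primary objectives. SAP 7.6 meanwhile still justifies 20 subjects partly by an initial estimate of efficacy.

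A reader who wants the result would have to count from listings and settle two questions that the SAP leaves open.

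- **What counts as a response.** The objective requires confirmation. The endpoint definition in protocol 12.1.2.1.2 asks only for a best overall response of CR or PR.
- **Which denominator applies.** The protocol offers three sets, and the SAP no longer defines two of them. With assumed counts of one responder among 6 enrolled, 4 of them evaluable, the answer is 1/6 = 16.7% or 1/4 = 25%.

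SAP 4 says that describing the analyses in advance is meant to prevent this kind of after-the-fact choice.

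**Working it through.** **No plan figure to reproduce.** The 20 subjects (6 in the run-in) rest on clinical grounds. The documents give no alpha, power or responder threshold.

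**Inputs.** The reference ORR for ipilimumab alone is about 14%, and an ORR above 20–30% would count as supportive (protocol 6.3). The method is Clopper-Pearson 95% (protocol 12.1.6). The first scan is at week 9 (± 7 days), the confirming scan comes at least 4 weeks later, and imaging ends at study termination (protocol 11.3.1.1). The numbers enrolled, scanned and responding are not given, so n = 6, 12 and 20 are assumptions.

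**Step 1: can the interval be computed?** For x responders among n, the lower limit is the 2.5% quantile of Beta(x, n−x+1) and the upper limit is the 97.5% quantile of Beta(x+1, n−x). With x = 0 the lower limit is 0 and the upper limit is 1 − 0.025^(1/n). The interval exists for any n of 1 or more.

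| n (assumed) | Responders | ORR % | 95% interval % |
|---|---|---|---|
| 6 | 0 | 0 | 0–45.9 |
| 6 | 1 | 16.7 | 0.4–64.1 |
| 6 | 4 | 66.7 | 22.3–95.7 |
| 12 | 0 | 0 | 0–26.5 |
| 12 | 1 | 8.3 | 0.2–38.5 |
| 12 | 5 | 41.7 | 15.2–72.3 |
| 20 | 1 | 5.0 | 0.1–24.9 |
| 20 | 2 | 10.0 | 1.2–31.7 |
| 20 | 4 | 20.0 | 5.7–43.7 |
| 20 | 6 | 30.0 | 11.9–54.3 |
| 20 | 7 | 35.0 | 15.4–59.2 |

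**Step 2: how informative is it?** The smallest count with a lower limit above 14% is 4 of 6, 5 of 12 or 7 of 20. If the true ORR were 30%, the binomial probability of reaching that count is 0.070, 0.276 or 0.392. If it were 14%, the probability is 0.005, 0.018 or 0.015.

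**Step 3: what does early termination do?** On scheduled scans a confirmed response takes 9 + 4 = 13 weeks (12 if the first scan is a week early). Subjects cut off before then cannot count as confirmed responders. Suppose the true ORR is 30% and half of responses can be ascertained. The expected FAS ORR is then 0.30 × 0.5 = 15%. From the table, the upper limit falls below 30% only with 0 responders at n = 12, and only with 0 or 1 at n = 20.

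- n = 12: 0.85^12 = 0.14, against 0.70^12 = 0.014 with full ascertainment.
- n = 20: 0.85^20 + 20 × 0.15 × 0.85^19 = 0.039 + 0.137 = 0.18, against 0.70^20 + 20 × 0.30 × 0.70^19 = 0.001 + 0.007 = 0.008.

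An interval that appeared to exclude 30% could therefore be a result of stopping scans. The Clopper-Pearson limits cover sampling error only.

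**The case against.** The strongest reply is that the sponsor stated the change three times, gave a reason and recorded it as a deviation. The trial is single-arm and descriptive, safety is still summarized, and by-subject listings are promised. An ORR biased downward by termination, with a very wide interval, could mislead more than it informs. Best-response counts without a proportion would avoid that.

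Much of this stands. A reader might infer that an unfavorable primary result was hidden or that the response data were lost. The documents support neither: the deviation is declared, and the protocol requires the data to be recorded and listed. A reader might also think that the FAS was always the ORR denominator. The synopsis gives that place to the Efficacy Evaluable Set, so a FAS table is itself a change to be disclosed. Nor is the protocol silent on subjects without a first scan: section 12.1.1 has evaluability rules for early progression and early death, though the SAP does not carry them over.

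Two parts do not stand. Declaring an omission does not make it necessary; limited data and early stopping are sound reasons to drop Kaplan-Meier analyses, but not a count. And counts alone would leave readers to form the proportion themselves, without the warning that a footnote can attach to it.

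**Conclusion.** The point holds as incomplete reporting of a primary objective. The SAP gives no summary of confirmed ORR, although the planned method works at any sample size, the FAS is still defined, and the protocol requires the response data on the eCRF. It is worth fixing because the remedy is specific and cheap.

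Its size is modest. At the assumed sizes of 6, 12 and 20, the lower limit would exceed 14% with probability 7%, 28% or 39% even if the true ORR were 30%. A reader might take 0/12 or 1/20 as ruling out 30%, or read the table as a comparison with ipilimumab alone. Neither is justified, given the ascertainment bias and the absence of a control arm or stated threshold.

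Confidence is medium. The documents do not say how many subjects were enrolled, scanned or responding. A count table can always be produced, but whether its ORR would be interpretable is unknown.

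**What to change.** Replace the blanket omission in SAP 6.4.1.1, 7.4.1 and 7.7 with one descriptive table on the FAS. SAP 7.1.1 already sets the layout: "Tables and figures will be summarized by treatment group".

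- **Rows.** Use mutually exclusive best overall response per RECIST 1.1: confirmed CR, confirmed PR, SD, PD, and not evaluable with the reason (such as no post-baseline scan or study termination). Show unconfirmed CR or PR as an of-which count, not as a further row. Such a subject may also qualify as SD, whose minimum duration is 7 weeks (protocol Appendix 4).
- **Estimate.** Give confirmed CR plus PR over all FAS subjects with the Clopper-Pearson 95% interval. State the number with a post-baseline assessment, so that the protocol's Efficacy Evaluable denominator can also be seen.
- **Footnote.** Subjects cut off by termination count as non-responders, which pulls the proportion down. The interval covers sampling error only. It must not be read as excluding any target ORR or as a comparison with ipilimumab alone.
- **SAP 7.7.** Record as deviations the move from the Efficacy Evaluable Set to the FAS, the non-responder rule, and the efficacy analyses still dropped (such as Kaplan-Meier PFS, OS and DOR).

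The cost is SAP wording and one table from data the protocol already requires; visits, treatment and data collection do not change. The drawback is a wide interval, close to uninformative if only about six subjects were enrolled. The all-enrolled denominator should add little distortion beyond termination itself, because protocol 11.1 dates enrollment at the start of treatment, so enrolled and treated subjects should nearly coincide.
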